Synopsis Trial Schematic 4.1.1 Screening/Baseline Period 9.2 Sample Size Determination	Added flexibility for total number of subjects required for trial	This is an exploratory trial. With the target trial population of patients with dementia-related apathy, a sample size between 60 and 75 should provide sufficient data to assess effect of CVL-871 without undue delay
Synopsis 9.2 Sample Size Determination	In sentence referring to extending enrollment due to higher anticipated early terminations, removed language “due to COVID-19 or other reasons”	Modification due to impacts from COVID pandemic no longer necessary
Trial Schematic Schedule of Assessments 4.1.2 Treatment Period 6.2 Preparation/Handling/Storage/Accountability/Disposition	Modified such that Visits 3, 4, and 7 will only be conducted on site	Option for remote visits to accommodate potential issues due to COVID-19 pandemic no longer necessary
Schedule of Assessments 4.1.1 Screening/Baseline Period	Added information that extension of screening period beyond 30 days is permitted in rare cases with medical monitor approval	Additional flexibility needed due to length of screening/baseline visit and need for caregiver to also be present at visits
Schedule of Assessments 4.1.2 Treatment Period	Removed psychosocial intervention	Reduce burden in elderly patient population
Schedule of Assessments 4.1.2 Treatment Period	Removed 4-hour post-dose observation period at Visit 3 and Visit 4	Reduce burden for elderly patient population. Visits 3 and 4 will be conducted in clinic; subjects will be monitored following dosing while concurrently undergoing scheduled assessments
Schedule of Assessments	Added clarification that prolactin results will be “partially” blinded	Procedural clarification
5.1 Inclusion Criteria	Modified such that total body weight has to be greater than or equal to 50 kg (110 lbs)	Mathematical inconsistency as 50 kg is 110.2 lbs
5.2 Exclusion Criteria	Removed sentence regarding exclusion of subjects with symptoms of agitation or aggression that are being controlled using SSRIs/SNRIs from Exclusion #1	Maintain consistency with changes made to prior/concomitant medications permitted

Section # and Name	Description of Change	Brief Rationale
5.2 Exclusion Criteria	Added to Exclusion #1 that anxiety or depressive symptoms secondary to dementia or other medical condition are not exclusionary provided they are not the primary diagnosis and are stable	Updated to be more reflective of proposed target patient population
5.2 Exclusion Criteria	Modified exclusionary scores on NPI for other NPI subdomains of disinhibition, agitation/aggression, delusions, and hallucinations in Exclusion #4	Update to be more reflective of proposed target patient population
5.4 Screen Failures	Modified to allow for more than 1 rescreening to be conducted with medical monitor approval	Increase flexibility needed for elderly patient population
6.5.2 Prohibited Medications	Reduced period required for stable doses of cholinesterase inhibitors, memantine, and SSRI/SNRIs to 60 days	Update to be more reflective of medication use in proposed target patient population
6.5.2 Prohibited Medications	Removed requirements for dosage and indication (agitation/aggression) for SSRI/SNRI use	Update to be more reflective of medication use in proposed target patient population
6.5.2 Prohibited Medications	Added that pregabalin and gabapentin are prohibited unless being used to treat pain, dose has been stable for at least 60 days prior to randomization, and dosage does not exceed recommended limits per US Package Insert	Update to be more reflective of medication use in proposed target patient population
6.5.2 Prohibited Medications	Added armodafinil to list of prohibited prior and concomitant medications	Update to be more reflective of medication use in proposed target patient population
6.5.2 Prohibited Medications	Added in dose limits for age/sex for nonbenzodiazepine sleep agents	Update to be more reflective of medication use in proposed target patient population
6.5.2 Prohibited Medications	Moved footnote regarding additional information on use of nonbenzodiazepine sleep aids into body of table.	Increase prominence of important information so not inadvertently overlooked
6.5.2 Prohibited Medications	Revised wording regarding prohibited nutritional supplements and herbal preparations to indicate these are restricted due to potential CYP3A4 drug-drug interactions rather than central nervous system effect; remove omega 3 fatty acids	Based on literature that these supplements do not have known central nervous system effect and removal of omega 3 fatty acids as it does not interact with CYP3A4

1 PROTOCOL SUMMARY

1.1 Synopsis

Sponsor Name: Cerevel Therapeutics, LLC

Name of Investigational Medicinal Product: CVL-871

Protocol Title: A Randomized, Double-blind, Placebo-controlled Trial to Evaluate the Safety, Tolerability, and Pharmacodynamics of CVL-871 in Subjects With Dementia-Related Apathy

Short Title: A Trial of the Safety, Tolerability, and Pharmacodynamics of CVL-871 in Subjects With Dementia-Related Apathy

IND Number: 150,086

Trial Phase: 2a

Treatment/Indication: Treatment of dementia-related apathy

Rationale: CVL-871 is a dopamine D1/D5 receptor partial agonist that is being evaluated for the treatment of dementia-related apathy. The aim of this trial is to evaluate the safety, tolerability, and pharmacodynamics of CVL-871 in subjects with dementia-related apathy.

Objectives and Endpoints

Objective	Endpoint
Primary	

 To assess the safety and tolerability of 2 fixed doses of CVL-871 in subjects with dementia-related apathy 	
 Incidence and severity of TEAEs Clinically significant changes in ECG results, clinical laboratory evaluations, vital sign measurements, and physical and neurological examination results Clinically significant findings in suicidality assessed using the C-SSRS
Secondary	

 To assess the pharmacodynamic effects of 2 fixed doses of CVL-871 on apathy in subjects with dementia-related apathy 	
 Change from baseline to Visit 5 (Week 6) and Visit 6 (Week 12) in the following: 
 NPI-C apathy domain score NPI apathy domain score DAIR score AES-C score
Exploratory	

 To evaluate the plasma concentrations of CVL-871 in subjects with dementia-related apathy 	
 Plasma concentrations of CVL-871 at Visits 2 (Week 1), 4 (Week 3), 5 (Week 6), and 6 (Week 12)

 To evaluate the effect of CVL-871 neuropsychiatric symptoms other than apathy 	
 NPI-C dysphoria domain score NPI domain scores (other than apathy)

 To assess the effects of 2 fixed doses of CVL-871 on cognition in subjects with dementia-related apathy 	
 Change from baseline to Visit 6 (Week 12) in the ADAS-Cog13 score

 To assess the effects of 2 fixed doses of CVL-871 on functional assessments (eg, activities of basic living, and cognitive, functional, and behavioral performance) in subjects with dementia-related apathy 	
 Change from baseline to Visit 5 (Week 6) and Visit 6 (Week 12) in the following: 
 mADCS-CGIC scores mCGI-S scores CaGI-S scores CaGI-C scores

 Investigate the impact of COMT (Val-Met) status on safety and pharmacodynamics 	
 Evaluation of safety and pharmacodynamic endpoints in subgroups of subjects based on their COMT (Val-Met) status

Abbreviations: ADAS-Cog13 = Alzheimer's Disease Assessment Scale – Cognition 13-item scale; AES-C = Apathy Evaluation Scale-Clinician; COMT = catechol-O-methyltransferase; C-SSRS = Columbia-Suicide Severity Rating Scale; DAIR = Dementia Apathy Interview and Rating; ECG = electrocardiogram; mADCS-CGIC = modified Alzheimer's Disease Cooperative Study–Clinical Global Impression of Change; CaGI-C = Caregiver Global Impression–Change Scale; CaGI-S = Caregiver Global Impression–Severity Scale; mCGI-S = modified Clinical Global Impression–Severity Scale; NPI = Neuropsychiatric Inventory; NPI-C = Neuropsychiatric Inventory-Clinician; TEAE = treatment-emergent adverse event.

Overall Design:

This is a Phase 2a, multicenter, randomized, double-blind, placebo-controlled, parallel-group, 12-week trial to evaluate the safety, tolerability, and pharmacodynamics of 2 fixed doses of CVL-871 (1.0 mg daily [QD] and 3.0 mg QD) in male and female subjects aged 50 to 85 years who have dementia-related apathy.

The trial will include a 30-day Screening Period, a 12-week Treatment Period, and a 4-week Safety Follow-up Period. Each subject will participate in the trial for up to approximately 20 weeks.

Disclosure Statement: This is a parallel-group treatment trial with 3 arms that are blinded to the subjects and the investigator.

Number of Subjects:

Approximately 150 subjects will be screened to achieve the target of approximately 75 subjects randomly assigned to treatment (25 per group).

The trial may be considered as complete and be closed out following the randomization of 60 subjects in the event of significantly slower recruitment rate than anticipated to avoid unduly long delay of the final analysis.

Key Entry Criteria:

- Male subjects and female subjects of nonchildbearing potential, ages 50 to 85 years, inclusive
- Meet the International Society for Central Nervous System Clinical Trials and Methodology Apathy Working Group diagnostic criteria for apathy in neurocognitive disorders and have clinically significant apathy defined as Neuropsychiatric Inventory (NPI) apathy domain frequency score of ≥ 2 and NPI apathy domain severity score of ≥ 2
- Clinical diagnosis of 1 or more of the following:
 - a) Possible or probable Alzheimer’s disease dementia according to the 2011 National Institute of Aging – Alzheimer’s Association score clinical criteria at the Screening Visit; diagnosis must be stable for at least 6 months
 - b) Frontotemporal dementia (FTD; behavioral variant FTD, semantic variant primary progressive aphasia, or nonfluent/agrammatic variant primary progressive aphasia)
 - c) Vascular dementia (ie, not vascular cognitive impairment) due to either of the following:
 - a. Large vessel or atherothromboembolic disease
 - b. Small vessel disease according to the diagnostic criteria for vascular cognitive disorders
 - d) Possible or probable dementia with Lewy bodies according to the revised criteria for the clinical diagnosis of probable and possible dementia with Lewy bodies

Intervention Groups, Trial Treatment, and Duration:

Subjects will be randomized in a 1:1:1 ratio to receive CVL-871 1.0 mg QD, CVL-871 3.0 mg QD, or placebo QD. The dose of CVL-871 will be titrated to the target dose using

a fixed titration scheme. Randomization will be stratified by use of allowed serotonin-norepinephrine reuptake inhibitor/selective serotonin reuptake inhibitor at the time of randomization (as applicable). The planned duration of treatment is 12 weeks. The investigational medicinal products (IMPs) will be taken orally.

Statistical Methods:

Sample Size Estimation: While formal hypothesis testing is not the key objective of this trial, a target sample size of approximately 75 subjects randomized in a 1:1:1 manner between the placebo and 2 CVL-871 arms should allow the trial to have approximately 80% probability to detect an effect size (treatment difference/population standard deviation [SD]) of 0.678 in change from Baseline on the NPI apathy domain score at Week 12 between an active dose group and placebo, at a 2-sided alpha = 0.2 level (ie, an 80% confidence interval excluding zero). A minimum sample size of 60 subjects randomized 1:1:1 to the 3 treatment groups would allow this exploratory trial to detect an effect size of 0.761 with 80% power at a 2-sided alpha level of 0.2, and thus would be considered adequate. A discontinuation rate of 20% was taken into consideration in the sample size calculations. As a reference, in the ADMET 1 trial (6 weeks of treatment with methylphenidate for apathy in Alzheimer's disease), an effect size 0.5625 (mean difference of 1.8 and SD of 3.2) on the change from baseline in the NPI apathy domain score was observed.

Statistical Methods: Descriptive statistical methods will be used to summarize the data from this trial. Pharmacodynamic endpoints with repeated post-baseline assessments will be analyzed for the modified intent-to-treat (mITT) population using a mixed-model repeated measures (MMRM) analysis, including baseline score (if applicable), treatment, concomitant selective serotonin reuptake inhibitor/serotonin-norepinephrine reuptake inhibitor use, visit, and the interaction between treatment group and visit as fixed factors in the model. Subject will be included as a random effect in the model.

The trial is designed as a learning trial instead of a confirmatory trial. The key research question for the pharmacodynamic endpoints will be primarily addressed with an estimand based on the following attributes: 1) treatments as randomized regardless of the final dose level achieved following the titration steps, 2) subjects in the mITT population who reach dose increases to at least Step 4 on Day 21 during titration as the target trial population, 3) change from Baseline to Week 12 as the key time point for assessing change from baseline in measured endpoints of interest, 4) the treatment differences estimated based on the least square mean and the corresponding 80% confidence interval from the MMRM model as the population level summary, and 5) a hypothetical strategy to address intercurrent events (ICEs) of potential death, treatment discontinuations, missed visits, and start of prohibited concomitant medications, unless a treatment-related reason can be identified for a given ICE. As the trial is of exploratory nature, a hypothetical strategy will be used to address the ICEs unless a treatment-related reason can be identified for an ICE. If such reasons are identified, a composite strategy may be taken, eg, assigning highest severity to the case, to ensure appropriate interpretation of the data. Further details, including additional estimands for the research questions on the

[figure not shown]
effect of combined CVL-871 treatment group versus placebo and on the effect of final dose levels of CVL-871 following the completion of titration versus placebo, will be described in the statistical analysis plan.

Safety Review Team:

A Safety Review Team will review the blinded safety data from this trial.

1.2 Schema

Figure 1 Trial Schematic

Abbreviations: AD = Alzheimer’s disease; DLB = dementia with Lewy bodies; ET = Early Termination; FTD = frontotemporal dementia; QD = once daily; VAD = vascular dementia.

1.3 Schedule of Assessments

Table 1 Schedule of Assessments

Trial Period	Screening Period ^{a,b}	Treatment Period (12 weeks)									Post-treatment Follow-up (4 weeks)	
		Visit 1	Visit 2/ Baseline	Visit 3 ^d	Contact	Visit 4 ^e	Contact	Visit 5	Contact	Contact	Visit 6/ ET ^f	Visit 7
Trial Day	-31 to -1	1	8	14 ^g /18	22	29	43	57	71	85	99	113
Trial Week			1	2	3	4	6	8	10	12	14	16
Window			±3 days			±5 days						
Entrance and History												
Informed consent ^h	X											
Assign subject number	X											
Eligibility criteria	X	X										
Medical and psychiatric history	X											
Demography	X											
History of drug and alcohol use	X											
DCA (electronic form) ⁱ	X											
MMSE (electronic form) ⁱ	X											
Randomization		X										
Pharmacodynamic and Other Endpoint Assessments												
Electronic Formsⁱ												
NPI	X	X					X			X		
NPI-C (apathy only)		X					X			X		
NPI-C (dysphoria)		X					X			X		
DAIR		X					X			X		

Trial Period	Screening Period ^{a,b}	Treatment Period (12 weeks)									Post-treatment Follow-up (4 weeks)	
Visit/Contact ^c	Visit 1	Visit 2/ Baseline	Visit 3 ^d	Contact	Visit 4 ^e	Contact	Visit 5	Contact	Contact	Visit 6/ ET ^f	Visit 7	Contact
Trial Day	-31 to -1	1	8	14 ^g /18	22	29	43	57	71	85	99	113
Trial Week			1	2	3	4	6	8	10	12	14	16
Window			±3 days			±5 days						
AES-C		X					X			X		
ADAS-Cog13		X								X		
mADCS-CGIC worksheet		X										
mADCS-CGIC ^j							X			X		
mCGI-S		X					X			X		
CaGI-S		X					X			X		
CaGI-C ^j							X			X		
Safety Assessments												
Physical/ neurological examination ^k	X									X		
ECG ^l	X	X	X		X		X			X	X	
Vital sign measurements ^m	X	X	X		X		X			X	X	
C-SSRS ⁿ (electronic form) ⁱ	X	X	X		X		X			X	X	
Prior/concomitant treatments ^o	←-----→											
Adverse event monitoring ^o	←-----→											
Laboratory												
Blood for safety laboratory sample	X	X	X		X		X			X	X	
Urine for safety laboratory ^p	X	X	X		X		X			X		

Trial Period	Screening Period ^{a,b}	Treatment Period (12 weeks)									Post-treatment Follow-up (4 weeks)	
Visit/Contact ^c	Visit 1	Visit 2/ Baseline	Visit 3 ^d	Contact	Visit 4 ^e	Contact	Visit 5	Contact	Contact	Visit 6/ ET ^f	Visit 7	Contact
Trial Day	-31 to -1	1	8	14 ^g /18	22	29	43	57	71	85	99	113
Trial Week			1	2	3	4	6	8	10	12	14	16
Window			±3 days			±5 days						
Prolactin level ^q		X								X		
Urine drug screening ^t	X											
Test for alcohol	X	X										
Hepatitis B, C, HIV	X											
PK blood sample ^s			X		X		X			X		
Blood collection for COMT genotyping ^t		X										
Blood samples for future biospecimen research ^u		X										
Other												
IMP dispensing ^v		X	X		X		X					
IMP compliance assessment ^v			X	X	X	X	X	X	X	X		

Abbreviations: AD = Alzheimer’s disease; ADAS-Cog13 = Alzheimer’s Disease Assessment Scale – Cognition 13-item scale; AES-C = Apathy Evaluation Scale-Clinician; COMT = catechol-O-methyltransferase; COVID-19 = coronavirus disease-2019; C-SSRS = Columbia-Suicide Severity Rating Scale; DAIR = Dementia Apathy Interview and Rating; DCA = diagnostic criteria for apathy; DLB = dementia with Lewy bodies; ECG = electrocardiogram; eCRF = electronic case report form; ET = early termination; FTD = frontotemporal dementia; HIV = human immunodeficiency virus; IMP = investigational medicinal product; IRT = interactive response technology; mADCS-CGIC = modified Alzheimer’s Disease Cooperative Study-Clinical Global Impression of Change; CaGI-C = Caregiver Global Impression–Change Scale; CaGI-S = Caregiver Global Impression–Severity Scale; mCGI-S = modified Clinical Global Impression–Severity Scale; MMSE = Mini-Mental State Examination; NPI = Neuropsychiatric Inventory; NPI-C = Neuropsychiatric Inventory-Clinician; PK = pharmacokinetic(s); SARS-CoV2 = severe acute respiratory syndrome coronavirus 2; VAD = vascular dementia.

a. Extension of screening may be allowed following discussion and documented approval by the medical monitor prior to the expiration of the Screening Period. Extension will only be granted in rare circumstances and the 30-day duration should be adhered to whenever possible.

- b. Individual sites may require subjects to have SARS-CoV2 testing done prior to randomization. SARS-CoV2 testing may be performed any time after randomization per the investigator's discretion.
- c. Contact with subject via phone call, internet/web, or other acceptable means of communication to check on their status.
- d. Subjects will be monitored during scheduled assessments following dosing and those who do not tolerate the increase to Step 3 dose may decrease back down to Step 2 dose. See [Section 4.1.2](#).
- e. Subjects will be monitored during scheduled assessments following dosing and those who do not tolerate the increase to Step 5 dose may decrease back down to Step 4 dose. See [Section 4.1.2](#).
- f. The assessments scheduled for Visit 6 are to be performed for any subject who early terminates from the trial.
- g. Subjects who receive the Step 3 dose increase (rechallenge) on Day 13 will be instructed to call the site on Day 14 (day after they again receive the Step 3 dose) to ensure that they can tolerate the rechallenge.
- h. Informed consent must be obtained before any trial-related procedures are performed.
- i. Assessments will be completed using electronic forms. However, if it is not possible to complete electronic form, then paper forms are permitted.
- j. All responses will be relative to the subject's condition at Visit 2/Baseline, prior to the first dose of IMP.
- k. Full physical and neurological examinations should be completed at Screening and Visit 6/ET. The physical examination should include weight at all time points and height at the Screening Visit only. Physical and/or neurological examinations can be done at any time point during the trial at the investigator's discretion.
- l. At Screening, a triplicate set of 12-lead ECGs is required to assess subject eligibility. A triplicate set of ECGs is 3 consecutive ECGs collected 1 to 2 minutes apart over a 5-minute period. At all other noted time points, a single ECG is required. All ECGs should be performed after the subject has been at rest in a supine/semi-recumbent position for approximately 3 minutes. See [Section 8.3.3](#) for more details.
- m. Vital sign measurements include blood pressure, heart rate, and body temperature. Duplicate blood pressure and heart rate measurements will be obtained sitting/supine (after 5 minutes of rest) followed by a single standing measurement (after 2 minutes of rising from sitting/supine position). At each visit, body temperature will be obtained once, at the time of the first blood pressure measurement.
- n. The "Baseline/Screening" C-SSRS form will be completed for all subjects at Screening to determine eligibility and the "Since Last Visit" C-SSRS form will be completed at the Baseline Visit to ensure that the subject continues to qualify for the trial. The "Since Last Visit" C-SSRS form will also be completed at all visits after Baseline.
- o. Adverse events (serious and non-serious) and concomitant medications should be recorded from screening through the subject's last visit.
- p. Dipstick urinalysis results are not to be recorded on the eCRFs; any clinically significant abnormality should be captured as an adverse event.
- q. Prolactin results will be partially blinded.
- r. A urine drug screen is required at screening; see the exclusion criteria for exclusions based on the urine drug screen. The urine drug screen can be conducted at any time during the trial at the discretion of the investigator.
- s. PK samples will be collected at all clinic visits except Day 1. The date and time of the most recent dose, the dose step, and the time of the blood draw will be recorded. For Visit 3 and 4, PK samples to be collected approximately 2 hours post dose. PK samples should be drawn just after the ECGs at all visits.

- t. Blood samples for genotyping are to be collected prior to initiation of dosing.
- u. Future biospecimen research sample is optional and is to only be collected if signed consent is obtained from the subject. Sample can be collected any time prior to initiation of dosing.
- v. The first dose of IMP (at the Baseline Visit) will be taken in the clinic; subjects will be dispensed IMP to take at home between visits. Subjects will be instructed to bring their IMP to each clinic visit and take their daily dose at the clinic on visit days. Compliance will be assessed through self-reporting by the subject and by tablet count.

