3 OBJECTIVES AND ENDPOINTS

Table 2 Objectives and Endpoints

Objectives and Endpoints

Objective	Endpoint
Primary	

 To assess the safety and tolerability of 2 fixed doses of CVL-871 in subjects with dementia-related apathy 	
 Incidence and severity of TEAEs Clinically significant changes in ECG results, clinical laboratory evaluations, vital sign measurements, and physical and neurological examination results Clinically significant findings in suicidality assessed using the C-SSRS
Secondary	

 To assess the pharmacodynamic effects of 2 fixed doses of CVL-871 on apathy in subjects with dementia-related apathy 	
 Change from baseline to Visit 5 (Week 6) and Visit 6 (Week 12) in the following: 
 NPI-C apathy domain score NPI apathy domain score DAIR score AES-C score
Exploratory	

 To evaluate the plasma concentrations of CVL-871 in subjects with dementia-related apathy 	
 Plasma concentrations of CVL-871 at Visits 2 (Week 1), 4 (Week 3), 5 (Week 6), and 6 (Week 12)

 To evaluate the effect of CVL-871 neuropsychiatric symptoms other than apathy 	
 NPI-C dysphoria domain score NPI domain scores (other than apathy)

 To assess the effects of 2 fixed doses of CVL-871 on cognition in subjects with dementia-related apathy 	
 Change from baseline to Visit 6 (Week 12) in the ADAS-Cog13 score

 To assess the effects of 2 fixed doses of CVL-871 on functional assessments (eg, activities of basic living, and cognitive, functional, and behavioral performance) in subjects with dementia-related apathy 	
 Change from baseline to Visit 5 (Week 6) and Visit 6 (Week 12) in the following: 
 mADCS-CGIC scores mCGI-S scores CaGI-S scores CaGI-C scores

 Investigate the impact of COMT (Val-Met) status on safety and pharmacodynamics 	
 Evaluation of safety and pharmacodynamic endpoints in subgroups of subjects based on their COMT (Val-Met) status

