On Day 22 (Visit 4), all subjects will take the Step 5 dose of IMP at the clinic. Subjects will be monitored for tolerability while undergoing concurrent assessments; after completion of all visit procedures, the investigator will assess whether the participant will continue with the new dose. Subjects who are unable to tolerate the dose at Step 5 may go back to the dose at Step 4 and continue on that dose for the remainder of the trial. Subjects who are able to tolerate the Step 5 dose will continue on this dose for the remainder of the trial and no further dosing adjustments are allowed.

[figure not shown]
Lack of tolerability should be of sufficient severity that it results in significant dysfunction or distress to the subject (eg, Common Terminology Criteria for Adverse Events [CTCAE] Grade 2/3). The medical monitor should be contacted in any instance

where the investigator is uncertain whether the subject is able to tolerate the stepwise dose increase.

No deviations in the dosing schedule, other than those noted above, are allowed.

The titration scheme, including the dosing decision time points, is presented in [Figure 2](#).

Figure 2 Dosing Schematic

Abbreviations: PBO = placebo.

Note: If “Yes” then continue with new dose; if “No” then stay at previous dose.

Assessments will be conducted at the Week 1, 3, 6, and 12 visits. Subjects will be instructed to take their dose of IMP at the clinic on days when visits occur. Blood samples for PK analysis will be collected at the Week 1, 3, 6, and 12 visits.

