4.3 Dosing Rationale

Significant improvements in apathy symptoms have been reported following treatment with methylphenidate in patients with AD (Rosenberg et al, 2013; Padala et al, 2018). As mentioned previously, CVL-871 is a D1/D5 receptor partial agonist and can provide

increased dopaminergic stimulation without the abuse liability and potential for cardiovascular and other systemic side effects associated with psychostimulants. The top dose of 3 mg QD CVL-871 has been demonstrated to provide improvement of motor symptoms in patients with Parkinson's disease (Gurrell et al, 2018). This dose was well tolerated and was achieved using a quick titration scheme in both healthy subjects and patients with Parkinson's disease. Based on in vitro estimates, this dose is expected to result in approximately 80% occupancy at target receptors in humans. The terminal elimination half-life of 24 hours is expected to provide stable plasma concentrations, approximately 2-fold peak-to-trough ratio, following QD dosing. Based on exposures from B7821001, 3 mg QD is the maximum dose that can be administered without exceeding the exposure limiting criteria based on nonclinical toxicological data.

The lower dose of 1.0 mg QD will provide the pharmacodynamic data at approximately 60% target occupancy. Data from these 2 doses will support evaluation of the dose relatedness of the response. It is important to acknowledge the potential that optimizing cortical D1 circuitry may show significant sensitivity to several factors beyond dose, including individual baseline dopaminergic state, genetics, central nervous system (CNS) disease and neurodegeneration, and concomitant medication that impact dopamine neurotransmission. Evaluation of 2 fixed doses with distinctly different levels of target occupancy in this exploratory trial will facilitate the determination of a dose range for D1 partial agonist therapy for dementia-related apathy in subsequent trials.

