10. PHARMACOKINETICS

Single blood samples will be collected in appropriately labeled tubes for determination of the concentration of CVL-871 in plasma at Weeks 1, 3, 6, and 12.

Plasma concentration data of CVL-871 will be summarized for each dose at each time point using descriptive statistics and graphs based on all randomized subjects who received at least one dose of IMP and had at least one measurable CVL-871 concentration result. Additionally, all data will be listed for PK set. The descriptive statistics for PK concentrations will include geometric mean and geometric coefficient of variation (GCV) in addition to the descriptive statistics described in [Section 4.4.5](#).

The geometric mean and GCV will be calculated based on the mean and variance of the logarithmic transformed data with the following formula to transform back:

Geometric mean = $\exp(\text{mean})$, and

CV = $100 * \sqrt{\exp(\text{variance}) - 1}$.

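### SAP 10 should summarise CVL-871 concentrations by actual dose step and hours since last dose, because Visits 5 and 6 have no nominal draw time and Visit 4 is not yet steady state for 3 mg

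*Protocol*

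**What the plan says.** **Sampling.** Protocol 1.3, footnote s, states "PK samples will be collected at all clinic visits except Day 1", which means Visits 3, 4, 5 and 6 (Days 8, 22, 43 and 85). It then gives a time for two of them: "For Visit 3 and 4, PK samples to be collected approximately 2 hours post dose". It also requires "The date and time of the most recent dose, the dose step, and the time of the blood draw will be recorded", and adds "PK samples should be drawn just after the ECGs at all visits". Footnote v has the daily dose taken in clinic on visit days. Protocol 8.7 puts the pharmacodynamic ratings ahead of the safety assessments. For Visits 5 and 6 nothing says whether the in-clinic dose comes before or after the draw.

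**Dosing.** Under Protocol 4.1.2 and Table 3, Visit 3 is the first Step 3 dose (1.0 mg in both active arms). Visit 4 is the first Step 5 dose: the first 3.0 mg dose in the 3 mg arm, and the same 1.0 mg as since Day 8 in the 1 mg arm. The section also provides: "Subjects who are unable to tolerate the dose at Step 5 may go back to the dose at Step 4 and continue on that dose". In the 3 mg arm, Step 4 is 2.0 mg. Table 3 ends dosing on Day 84.

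**Kinetics.** Protocol 4.3: "The terminal elimination half-life of 24 hours is expected to provide stable plasma concentrations, approximately 2-fold peak-to-trough ratio, following QD dosing".

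**Analysis.** SAP 10: "Plasma concentration data of CVL-871 will be summarized for each dose at each time point using descriptive statistics and graphs", with geometric mean and geometric CV added. SAP 4.4.3 classes data by the scheduled visit in the eCRF. No rule uses hours since dose. The exploratory endpoint is listed as "Plasma concentrations of CVL-871 at Visits 2 (Week 1), 4 (Week 3), 5 (Week 6), and 6 (Week 12").

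**The concern.** A concentration has meaning only with its dose and its time since dose. The two visits with a nominal time fall on the first day of a step. The two visits at steady state have no nominal time, and the planned summary does not use the recorded times in its place.

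Protocol 4.3 says the two doses are meant to support evaluation of dose-relatedness, and that 3 mg is the highest dose within the exposure limit. These summaries are where a reader would look for the exposure actually reached. A table by visit could show a change between Week 3, Week 6 and Week 12, or a shortfall from dose proportionality, that comes only from the draw clock or the titration schedule.

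**Working it through.** **Inputs.** Doses by day come from Protocol Table 3, and the 24 h half-life from Protocol 4.3. Not in the documents, and therefore assumed: one compartment, linear kinetics and, in the base case, immediate absorption. The time of peak concentration is not given, so whether 2 h is the peak cannot be checked.

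**1. The plan's own figure.** Peak-to-trough at steady state = 2^(24/24) = 2.00, which agrees with the stated 2-fold. Accumulation = 1/(1 − 1/2) = 2.

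**2. Formula.** Concentration (in mg-dose units) = Σ dose × 2^(−h/24), where h is hours since each dose. At 2 h the decay factor is 2^(−2/24) = 0.944.

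**3. Visit 3 (Day 8), both active arms.** Residual before the dose = 0.5 × (1/2 + 1/4 + 1/8 + 1/16) + 0.25 × (1/32 + 1/64 + 1/128) = 0.482. With the 1 mg dose: 1.482 × 0.944 = 1.399. Steady state on 1 mg: 2 × 0.944 = 1.888. Fraction = 1.399/1.888 = **0.74**, the same in both arms.

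**4. Visit 4 (Day 22).**
- 3 mg arm: 3 + 2 × (1/2 + … + 1/32) + 0.031 from the earlier 1 mg doses = 4.969; × 0.944 = 4.690. Steady state: 6 × 0.944 = 5.663. Fraction = **0.83**.
- 1 mg arm: the fifteenth consecutive 1 mg dose, 1.888. Fraction = **1.00**.
- Arm ratio = 4.690/1.888 = **2.48**, against 3.00 at steady state.

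**5. Sensitivity.** Half-life 18 to 36 h, with absorption immediate or at 0.5 to 2 per hour: Visit 3 fraction 0.60 to 0.80; Visit 4 fraction in the 3 mg arm 0.73 to 0.87; Visit 4 arm ratio 2.19 to 2.60.

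**6. Visits 5 and 6.** Both arms are at steady state (Day 43 is 21 days after Day 22). Level relative to peak, by hours since dose:

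| Hours | 0 | 2 | 6 | 12 | 24 |
|---|---|---|---|---|---|
| Level | 1.00 | 0.94 | 0.84 | 0.71 | 0.50 |

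With no change in clearance, Week 6 over Week 3 in the 3 mg arm reads 5.663/4.690 = 1.21 if Week 6 is drawn at 2 h, and 3.000/4.690 = 0.64 if drawn at 24 h.

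**7. Effect on the geometric CV (bounding case).** If half the draws are at peak and half at trough, SD of the log = ln 2/2 = 0.347, and timing alone gives a CV of √(exp(0.347²) − 1) = 35.7%. This combines with between-subject variation on the log-variance scale. For an illustrative 40% CV: ln(1.16) + 0.120 = 0.148 + 0.120 ≈ 0.269, a total CV of 55.5%.

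**8. Step-down.** A subject on 2 mg who is tabulated under 3 mg reads 2/3 of the expected level, or 33% low.

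**9. Visit 6.** Table 3 ends dosing on Day 84; Visit 6 is Day 85; footnote v has dosing in clinic on visit days. On the first reading the draw is about 24 h post dose (0.50 of peak). On the second it may follow a same-day dose. If Visit 5 is drawn at 2 h and Visit 6 at 24 h, the two differ by 0.944/0.500 = 1.89-fold with no change in exposure.

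**The case against.** The strongest reply is that nothing is lost. Footnote s has dose time, dose step and draw time recorded for every sample, so each Visit 5 or 6 concentration can be placed on the dosing interval. This stands. A reader might infer that steady-state exposure at 3 mg cannot be read from this trial. The documents do not support that: the gap is in the planned summary, not in the data.

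A reader might also infer that the arms are compared at unequal states throughout. That is true at Visit 4 only. At Visit 3 both active arms have had identical doses, and at Visits 5 and 6 both are at steady state. No arm ratio, peak, trough or AUC is planned.

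On the 2 mg subjects, SAP 10 says dose, not treatment group; the SAP 4.3 PK set uses actual treatment; SAP 13.1 already tabulates adverse events by actual dose level, including 2 mg; and the table shells are a separate document. On the other side, the treatment labels in SAP 4.4.1 offer only 1.0 mg and 3.0 mg. The wording is ambiguous, so the 33% applies only if assigned dose is meant.

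On safety, vital signs and ECGs come shortly before the draw (Protocol 8.3), so the recorded times approximately date those readings too. No primary endpoint depends on a timed concentration.

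Finally, SAP 1 says enrollment closed by a November 2024 decision, so a change to the sampling schedule is probably too late. That also stands, and leaves the SAP as the place to act.

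**Conclusion.** The point holds as a gap in the PK summary. Followed as written, SAP 10 can pool steady-state samples up to about 2-fold apart on timing alone, and does not say whether stepped-down subjects count as 2 mg or 3 mg. The Week 3 summary sets a 3 mg arm at about 83% of steady state (0.73 to 0.87) beside a 1 mg arm at 100%, so the ratio a reader would form is about 2.5 (2.19 to 2.60) and not 3.

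These figures rest on the stated half-life and on assumed linear one-compartment kinetics. The 2-fold figure is the protocol's own. It would be wrong to say that mixed timing adds 36 percentage points to the CV: log-variances add, and half peak, half trough is an extreme. PK is exploratory, so the effect is on descriptive exposure and any later exposure-response reading, and not on the primary safety objective.

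**What to change.** In SAP 10, before database lock:

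- Summarise concentrations by actual dose step at the draw, with a 2 mg row, and by hours since last dose from the recorded times, for example up to 6 h and about 24 h. Show other draws separately. Within the first band, timing alone spans at most 1/0.84 = 1.19-fold in the base case.
- Label Week 1 and Week 3 as first-dose-of-step values, noting that the 1 mg arm is already at steady state at Week 3. Take steady-state exposure from Week 6 and Week 12.
- Show early-termination draws separately from Week 12, because Protocol 1.3, footnote f, uses the Visit 6 assessments for both.

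In the endpoint tables (Protocol 1.1 and 3, SAP 2), change the Week 1 PK visit from Visit 2 to Visit 3: the schedule puts Week 1 at Visit 3, and footnote s excludes Day 1.

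Reconcile Table 3, the Day 85 visit and footnote v, so that the Visit 6 draw has a known place in the dosing interval. A nominal draw time at Visit 5 is worth adding only if such visits remain.

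The cost is a few SAP lines using data already collected. The downside is smaller cells in some dose-by-time rows.
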